12. POTENTIAL BENEFITS TO SUBJECTS

Subjects may not receive any direct benefits from participating in this study. Potential benefits to subjects include the opportunity to reflect on their mental health and alcohol use, their beliefs about treatment, and any perceived barriers to treatment in a structured intervention session with a Deaf counselor. In addition, subjects will be provided a list of resources for seeking mental health and/or substance use treatment, as well as practical support in identifying available treatment options, scheduling treatment sessions, and problem-solving barriers to treatment (e.g., accommodations). This support may directly connect subjects with professional treatment for their symptoms. Finally, Deaf individuals are often not consulted for their opinions about services rendered within their own community. Therefore, by being asked for input on future interventions and services for Deaf people, Subjects may experience increased feelings of empowerment and self-efficacy. Given the minimal risks associated with the proposed research and the potential gains both to the individual and Deaf individuals more broadly, the benefits appear to outweigh the risks.

Importance of the Knowledge to be Gained: There is an urgent need to identify interventions that may increase treatment-seeking among Deaf individuals with behavioral health disorders in order to begin addressing current health disparities. If shown effective, CBT-TS may be a promising intervention that could be disseminated within the Deaf community. Results will provide the necessary preliminary data to refine CBT-TS for Deaf individuals and proceed to a randomized controlled trial (RCT) by collecting evidence of the acceptability of the intervention, feasibility of the protocol, and preliminary evidence of the intervention's efficacy.

The proposed study will also provide a reproducible method for adapting evidence-based treatments and provide guidance on how to successfully conduct RCTs within the Deaf community. As such, this work will inform investigators across disciplines and, therefore, has the potential to improve multiple facets of Deaf people's health and wellness across the nation.

13. COSTS FOR PARTICIPATION

There are no costs to subjects.

14. PAYMENT FOR PARTICIPATION

Baseline Assessment: Subjects will be paid \$75 after completing the baseline assessment.

Follow-up Assessment: Subjects will be paid \$75 after completing the follow-up assessment.

Subjects will be paid via check.

15. SUBJECT WITHDRAWALS

Subjects will be advised during the consent process that they have the right to withdraw from the study at any time without penalty. If a subject chooses to withdraw from the study the data collected up until their withdrawal will be used for data analyses. Subjects may be removed from the study if they experience significant distress during the screening and baseline assessments or the intervention session. Withdrawn and removed subjects will be replaced.

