4. STUDY DESIGN

This is a Stage 1A intervention refinement study (Onken et al., 2014) to assess the acceptability, feasibility, and preliminary efficacy of CBT-TS for Deaf Individuals to improve professional treatment-seeking among Deaf adults with mental health and/or alcohol use problems. This study aims to identify clinical factors and formulate theories relevant to the intervention refinement (i.e., acceptability and feasibility data gathered through the trial) and further refine, modify, or adapt the intervention to boost its effects or ease of implementation for the given population. This goal will be accomplished through a single-arm, open pilot trial with a small sample of the new target population (i.e., Deaf individuals with behavioral health problems who are not currently engaged in treatment).

Interested subjects will be provided with an overview of the project goals and a detailed description of the screening procedures. Subjects will give verbal consent to participate in the screening assessments. Eligible subjects will then be invited to participate in the written

informed consent process for enrollment in the study. Upon enrollment in the study, all subjects will complete baseline assessments and then engage in the CBT-TS intervention via Zoom. One month after completing the intervention, all subjects will complete a follow-up assessment.

The main outcome data will include quantitative and qualitative feedback regarding the acceptability and feasibility of the intervention (i.e., recruitment and retention data, a client satisfaction survey, and qualitative subject feedback provided during the follow-up assessment), and clinical outcomes from the intervention (i.e., whether subjects scheduled professional treatment, and changes in subjects' perceptions towards treatment and intentions to seek treatment). Subjects' symptom severity at baseline and the follow-up assessment will also be examined to see how this data relates to treatment-seeking behaviors. The quantitative and qualitative subject feedback and the clinical outcome data will be used to refine the intervention content, materials, and procedures to enhance the intervention's efficacy for Deaf individuals.

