Lastly, to obtain quantitative and qualitative feedback about CBT-TS for Deaf Individuals, subjects will complete the Client Satisfaction Questionnaire (CSQ-8) and a semi-structured interview including several open-ended questions about the intervention measure, content, materials, and delivery, including its appropriateness for use with the Deaf community, the acceptability of the techniques, and the usefulness of the content and materials. As these questions will be asked one month after the subjects complete their intervention session, study personnel will provide descriptions of each of the intervention procedures and show subjects the intervention materials again to refresh their memory of their experience as they provide feedback on the intervention. The interviewer will take notes of the subjects' responses to the structured questions and enter this data into REDCap after the session. The paper copies of the subjects' responses will be stored in a locked cabinet in the PI's locked office in the Department of Psychiatry at URMC.

The follow-up assessment will be video recorded on Zoom. The recordings will be stored on Box.com.

Sharing Results: Subjects will be given the opportunity to receive a summary of the results from the trial. If interested, subjects will be asked to check a box at the end of the written consent form to give the research team permission to contact them after the completion of the study. The research team will prepare a brief written and signed summary of the main findings from the trial and email this information to the interested subjects.

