- c. Subject distress: Risks associated with subject burden or distress will be minimized by employment of research personnel with appropriate background and experience with psychological factors and Deaf subjects. Study personnel have specialized training in working with Deaf individuals who have behavioral health problems and are capable of providing support as needed throughout the study to manage mild to moderate reactions of distress that may arise. In the rare situation that a subject experiences a more severe reaction of distress during the course of the study, study personnel will evaluate the subject's emotional state and safety. Study personnel will briefly attempt to de-escalate the patient's distress. If these measures do not effectively reduce the patient's distress within 10-15 minutes and depending on the severity of the patient's distress, study personnel will contact the PI and the PI's mentor, [name] [name]. Together, the team will take appropriate actions to reduce the individual's risk for suicide, including developing a safety plan, contacting treatment professionals, friends, family members, and/or emergency services if needed, and referring the individual to mental health services.

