17. DATA AND SAFETY MONITORING PLAN

Safety Monitoring: Given that this study presents no more than minimal risk, data and safety monitoring will be the responsibility of the study PI, in consultation with the PIs' mentoring team. Individual subject data will be monitored by the PI and study personnel over the course of the study to identify any subjects who may need additional support. Alcohol use, and symptoms of post-traumatic stress disorder (PTSD), depression, suicidal risk, anxiety, and insomnia will be assessed at screening, baseline, and one-month follow-up assessments. If at any time a subject is identified by study personnel or the PI as having a serious psychiatric or alcohol use problem that requires immediate and intensive treatment (i.e., danger to self or others), this concern will immediately be reported to the PI and the PI's primary mentor, who will provide support, referral, and bridging to appropriate treatment options for stabilization. Should a subject present at a study session under the influence of drugs or alcohol, study personnel will be trained to discontinue the session, reschedule the session for a later date, and work with the subject to ensure they are in a safe place (i.e., at home, with family or friends, etc.). Should a subject communicate distress and intent to withdraw from the study, the PI will provide the subject with a list of

Deaf treatment resources to help the individual locate possible treatment options in their area.

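### A subject removed from the study for distress at an intervention session would, on the natural reading, miss the one-month visit, which holds all the acceptability data and the only scheduled later symptom check.

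*Combined protocol and SAP*

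**What the plan says.** Section 15 sets the removal rule: "Subjects may be removed from the study if they experience significant distress during the screening and baseline assessments or the intervention session". The next sentence reads: "Withdrawn and removed subjects will be replaced". The only rule there on data from people who leave is written for those who leave by choice: "If a subject chooses to withdraw from the study the data collected up until their withdrawal will be used for data analyses".

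Two places time the follow-up visit. Section 4 says: "One month after completing the intervention, all subjects will complete a follow-up assessment". Section 9 (Follow-up Assessment) has staff contact subjects one month after their last intervention session. The one exception it handles is a subject who does not complete the optional second session.

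The visit repeats the behavioral health measures and the D-PASS and adds the treatment utilization survey. At the same visit, "subjects will complete the Client Satisfaction Questionnaire (CSQ-8) and a semi-structured interview including several open-ended questions about the intervention measure". Section 17 places the later safety measures there too: "suicidal risk, anxiety, and insomnia will be assessed at screening, baseline, and one-month follow-up assessments".

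On distress, Section 11(c) gives a management pathway that begins "In the rare situation that a subject experiences a more severe reaction of distress during the course of the study" and runs through de-escalation, contact with the PI and mentor, safety planning and referral. Section 17 adds: "Should a subject communicate distress and intent to withdraw from the study, the PI will provide the subject with a list of" Deaf treatment resources. It also requires adverse events to be reported to the PI and mentoring team, and follow-up plans for SAEs and for unresolved unexpected events. Reasons for missing data are to be tabulated and used in judging feasibility.

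**The concern.** This is a Stage 1A refinement study. Aim 1 measures acceptability and Aim 3 uses subject feedback to change the intervention. A subject whose session was stopped for distress is well placed to say what in it needs changing. Section 15 takes that person out of the study, not just out of the intervention, and enrols someone else instead. Their ratings and opinions would then be missing for a reason tied directly to how they experienced the session.

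The same visit holds the survey behind the primary clinical outcome (whether treatment was scheduled) and the only scheduled symptom and suicidal-risk assessment after the intervention. Distress at screening or baseline is a different matter: those subjects have not received the intervention and have no view of it to give.

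**Working it through.** **Step 1: does a removed subject have a one-month visit?**

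- Section 4 promises the visit to all subjects but counts it from completing the intervention. A subject stopped partway through session 1 has not completed it. For removal at the optional second session this argument is weaker, since session 1 was finished.
- Section 9 counts from the last intervention session, a clock that does not need a completed intervention. It does not mention removed subjects.
- Section 15 removes the subject from the study and replaces them. No section offers a removed subject a visit, and none forbids one.
- The nearest rule, in Section 17 for a distressed subject who intends to withdraw, provides a resource list and no assessment.

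The natural reading is that the visit does not take place, though the text is not explicit.

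**Step 2: what is lost?**

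- CSQ-8, interview and treatment utilization survey: each is given only at the one-month visit, so none is obtained.
- Scheduled symptom and suicidal-risk assessments after the intervention: 0 of 1.
- Section 10 allows session recordings to be used for analysis, and Section 9 has the interventionist take notes. Neither gives the subject's own rating, and Section 18 does not list them as Aim 3 data.

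**Step 3: scale.** The plan has no figure to reproduce. Section 5 gives N = 45; no removal rate is stated. Assume k = 1, 3 or 5 removals at an intervention session, all replaced, with no other loss, so 45 + k subjects start.

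- Share of starters with no CSQ-8 = k/(45 + k).
- If half of those invited under the fix attend (assumed), the expected share is 0.5k/(45 + k).
- If removed subjects would rate an item 1 point lower (assumed), the observed item mean is too high by k/(45 + k) × 1.
- If 27 of the 45 followed subjects schedule treatment (60.0%, assumed), the proportion among all starters lies between 27/(45 + k) and (27 + k)/(45 + k).

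| k | Starters | No CSQ-8 | No CSQ-8, half attend | Item-mean shift | Scheduling among all starters |
|---|---|---|---|---|---|
| 1 | 46 | 1/46 = 2.2% | 1.1% | 0.02 | 27/46 to 28/46 = 58.7% to 60.9% |
| 3 | 48 | 3/48 = 6.3% | 3.1% | 0.06 | 27/48 to 30/48 = 56.3% to 62.5% |
| 5 | 50 | 5/50 = 10.0% | 5.0% | 0.10 | 27/50 to 32/50 = 54.0% to 64.0% |

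The chance of at least one removal among 45 subjects is 1 − (1 − p)^45. For assumed rates p of 2%, 5% and 10% it is 0.60, 0.90 and 0.99. Even a low rate therefore makes it more likely than not that the rule is used at least once.

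**The case against.** The strongest reply is that the documents are silent, not exclusionary. Removal is optional, and a distressed subject who is not removed still has the visit. The Section 9 clock runs from the last session, and Section 17 provides for follow-up contacts after missed sessions. This stands as far as it goes: a reader might infer that the plan bars removed subjects from follow-up, and it does not say that. It does not remove the problem, because nothing tells staff to invite someone who has been taken out of the study and replaced.

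A reader might also infer that removed subjects lose all safety follow-up. The documents do not support that. Acute management, reporting of adverse events (which include distress), and follow-up plans for SAEs and unresolved unexpected events all remain. Study-associated SAEs are reportable until 14 days after the subject goes off study. If removal counts as the off-study date, however, that window closes before the one-month mark, and no contact is scheduled within it.

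Nor should Section 17 be read as showing that a removed subject already has two of three symptom assessments. Under Section 9, screening stops at the first positive measure and baseline gives only the measures that remain, so each may have been given just once before the intervention.

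Finally, the numbers are assumed. Section 11 calls more severe distress rare and expects only mild reactions in sessions, so five removals would be surprising. Section 18 is descriptive with no go/no-go threshold, and no stated decision turns on a shift of 0.10 or less. All of this stands and limits the point to a minor one.

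**Conclusion.** The point holds as a minor design weakness. Followed as written, Section 15 can selectively lose the people who tolerated the session worst from the acceptability ratings, the interviews and the treatment-scheduling outcome. It can also cost them the one scheduled post-intervention symptom and suicidal-risk assessment. The main loss is their feedback.

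A reader might go further and infer that the acceptability or efficacy estimates will be materially biased. The documents do not support that, since no removal rate is given and the illustrated shifts are small. The conclusion rests on the natural reading of removal with replacement. If the study team already intends to invite these subjects, the change only writes that down.

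**What to change.** **Section 15.** Keep removal from the study for distress at screening or baseline. For intervention sessions, substitute wording such as:

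> If significant distress occurs during an intervention session, the intervention may be stopped. The subject remains in the study and is invited to the one-month assessment, timed from the stopped session, unless they decline or the PI judges contact unsafe. The minimum set is the PHQ-9 (with the P-4 if indicated), the treatment utilization survey, the CSQ-8 and brief feedback. Intervention materials are not shown again if this would cause distress. Stopped subjects may be replaced.

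**Section 18.** Report the number stopped or removed for distress. Use all subjects who started the intervention as the denominator for the completion percentages and for the Aim 2 proportion scheduling treatment, and state how many have an unknown outcome. Section 18 does not now name the completion denominator, so that part is a clarification.

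The acute management in Section 11 and the adverse-event rules in Section 17 need no change.

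**Cost.** Wording in two sections, which can go in one amendment. Each attendee costs $75 (Section 14) and one Zoom visit of staff time. For 1 to 5 attendees that is $75 to $375, or 2.2% to 11.1% of the 45 × $75 = $3,375 already planned for follow-up payments. The downside is a small burden on someone who has had a distress reaction; they may decline, and the reduced set and the PI's safety exception limit it.

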5. SUBJECT POPULATION

Subjects will be Deaf adults in the United States with clinically significant symptoms of AUD, PTSD, depression, and/or anxiety, who are not currently engaged in treatment, and whose primary method of communication is ASL or Pidgin Signed English (PSE).

Number: Forty-five subjects will be enrolled in the study.

Gender and Age: Subjects will be 18 years of age and older. Subjects will include all genders.

Race and Ethnic Origin: Based on pilot data, we expect that approximately 73% of the population will be White, 10% will be Black or African American, 6% will be Asian or Pacific Islander, 1 % will be American Indian or Alaskan Native, 10% will be Multiracial, and 13% will be Hispanic or Latinx.

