9. STUDY PROCEDURES

Screening Procedures: Recruitment materials will direct individuals to contact the research team via email or video phone to schedule a screening assessment with study personnel on Zoom. We will use procedures for screening that were successful in the PI's postdoctoral pilot study conducted at URMC. During the screening assessment, study personnel will briefly review the overall study goals and then explain the screening procedures to interested subjects. Study personnel will obtain verbal consent from interested subjects prior to proceeding with the screening assessment. This verbal consent will be documented in REDCap.

Subjects will be screened for eligibility using a (1) brief demographic survey, (2) several behavioral health measures including: the 10-item Alcohol Use Disorders Identification Test (AUDIT) to screen for AUD, 4-items from the National Survey of Drug Use and Health (NSDUH; Center for Behavioral Health Statistics and Quality, 2015) to determine if alcohol use within the past 30 days exceeds the limits for low-risk drinking adopted by NIAAA, the Patient Health Questionnaire-9 (PHQ-9) to screen for symptoms of depression, the Generalized Anxiety Disorder 7-item Scale (GAD-7) to screen for symptoms of anxiety, the PTSD Checklist for DSM-5 (PCL-5) to screen for symptoms of PTSD, and the Insomnia Severity Index (ISI) to screen for symptoms of sleep disturbance, and (3) screening items on the Alcohol Use Disorders and Associated Disabilities Interview (AUDADIS) to determine if there is any history of or current engagement in professional alcohol or mental health treatment.

The screening will begin with the demographics survey and then proceed to the behavioral health measures if the subject is eligible. The behavioral health measures will be administered to subjects in the order listed (see Sources of Research Materials below) until the subject screens positive on one of the measures. If the subject screens positive on one of the behavioral health measures, they will skip to the treatment engagement screening questions. If the subject does not screen positive on any of the behavioral health measures,

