The assessment and intervention sessions will be video recorded on Zoom. Research personnel will use a licensed URMC Zoom account which protects and encrypts all audio, video, and screen sharing data and supports HIPPA compliance. Subjects participating in the assessment and intervention sessions will be sent unique Zoom links for entering the Zoom meetings. Research personnel will use the waiting room feature to control subject access to the sessions and will lock the meetings after the subject joins the session. Following the sessions, the recordings will be directly uploaded to password protected drives on Box.com for secure storage. The recordings will be accessible only by IRB approved study personnel at URMC.

Publications or presentations resulting from this study will report only cumulative data or descriptions certain to maintain subjects' anonymity. Lastly, to minimize social and legal risks, this study contains a Certificate of Confidentiality to protect subjects' information. An explanation of the Certificate of Confidentiality is included in the informed consent form

- b. Identification of suicide ideation: Subjects will be screened for suicidal ideation using the PHQ-9, item 9. Subjects who endorse suicidal ideation will be administered a structured, validated follow-up assessment (P-4 Screener). Subjects who score as "high risk" on the P-4 Screener will be excluded from the study. Upon identification of a high risk for suicide, study personnel will provide support to the individual and contact the PI, [name], a licensed clinical psychologist with specialized training in working with Deaf individuals, including those at high risk for suicide, and [name] [name], a licensed clinical psychologist and expert in the prevention and treatment of suicide. Together, the team will take appropriate actions to reduce the individual's risk for suicide, including developing a safety plan, contacting treatment professionals, friends, family members, and/or emergency services if needed, and referring the individual to mental health services.

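### Do the replacement rule and the silence on removed subjects' data leave the feasibility denominators open?

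*Combined protocol and SAP*

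**What the plan says.** Section 5 states the sample size: "Forty-five subjects will be enrolled in the study". Sections 1 and 7 repeat 45. Section 7 presents it as a recruitment goal to be met within 12 months, at 3 to 4 subjects per month, with about 73% of those screened expected to be eligible.

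Section 15 has three relevant sentences:
- On voluntary exits: "If a subject chooses to withdraw from the study the data collected up until their withdrawal will be used for data analyses".
- On exits decided by the study: "Subjects may be removed from the study if they experience significant distress during the screening and baseline assessments or the intervention session".
- On both: "Withdrawn and removed subjects will be replaced".

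Section 11 has a further rule outside Section 15: subjects scoring as high risk "on the P-4 Screener will be excluded from the study". Section 17 lists when symptoms are measured: "suicidal risk, anxiety, and insomnia will be assessed at screening, baseline, and one-month follow-up assessments".

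On sequence, Section 4 says: "Upon enrollment in the study, all subjects will complete baseline assessments and then engage in the CBT-TS intervention via Zoom". Sections 4 and 8 place the eligibility decision at the end of screening, ahead of written consent. In Section 9 screening can stop early: "If the subject screens positive on one of the behavioral health measures, they will skip to the treatment engagement screening questions". Any measures not yet given move to the baseline visit.

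Section 18 (Aim 1) reports descriptive percentages: eligible, enrolled among eligible, and completing the intervention and follow-up. Aim 2 reports the proportion scheduling treatment after receiving CBT-TS. No analysis set is named. Section 17 requires reasons for missing data to be recorded, tabulated, reported and used in judging feasibility.

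**The concern.** Three things look loose when these sections are read together.

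1. A fixed enrolment of 45 and a replacement rule do not fit literally. One replacement after enrolment makes 46.
2. The data rule covers people who choose to leave. The next sentence creates a second kind of exit, removal for distress, and gives it no data rule.
3. The Section 11 exclusion has no stated time limit. Because screening stops at the first positive measure, a subject who is positive on the alcohol items could be enrolled before the PHQ-9, which triggers the suicide-risk screener, is asked. Section 18 does not say whether someone excluded at that stage is ineligible or is an enrolled non-completer.

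Aim 1 is acceptability and feasibility, and Section 12 says the results are to support a randomized trial. If subjects removed for distress or risk dropped out of the denominator and replacements took their places, completion would look better than it was. The removals are themselves feasibility information.

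**Working it through.** **The figure of 45.** The plan gives no power, precision or dropout calculation, so accrual is the only arithmetic behind 45. At 3 to 4 per month for 12 months, 3 × 12 = 36 and 4 × 12 = 48. The goal needs 45/12 = 3.75 per month, which is inside the range.

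**Effect of replacement on enrolment.** The documents give no exit rate, so I assume 3 post-enrolment exits, all replaced.
- Enrolled: 45 + 3 = 48, or 48/12 = 4.0 per month, the top of the stated range.
- Screened, at 73% eligible with all eligible subjects enrolling: 48/0.73 = 65.75, so about 66.

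**The two readings, if everyone else completes.**

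| Reading | Eligible | Completing |
|---|---|---|
| Exits stay counted as enrolled | 48/66 = 72.7% | 45/48 = 93.8% |
| Exits reclassed as ineligible | 45/66 = 68.2% | 45/45 = 100% |

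The completion gap is 100 − 93.8 = 6.2 points. The exact 95% interval for 45/48 is 82.8% to 98.7%. With one exit the comparison is 45/46 = 97.8% against 100%.

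**A heavier case.** Suppose 5 subjects withdraw and 5 are removed, all replaced, so 55 are enrolled. Completion is 45/55 = 81.8% over all enrolled. It is 45/50 = 90.0% if removed subjects alone are left out, and 100% if both groups are. The denominator could therefore matter if exits were common.

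**Which reading does the plan support?**
- *Eligibility.* Sections 4 and 8 settle it at the end of screening. The only later check before signature is decision-making capacity (Section 8). No section returns an enrolled subject to ineligible status, so the second row of the table has no basis in the text.
- *Completion.* Section 18 speaks of subjects without restriction. Section 15 keeps the data of those who withdraw. No section calls for a completers-only analysis or lets a replacement stand in for a leaver's record. All enrolled is the ordinary reading.
- *Removed subjects' data.* The text is silent, and no sentence says such data are discarded. Section 8 says the consent form covers retention and use of data; that form was not available for this review.
- *Enrolment count.* A goal plus a rule for making good losses means that replacements are additional. Section 15 also allows removal during screening; those subjects were never enrolled and add nothing to 45.

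**Scheduling proportion.** Section 18 ties it to subjects who have received the intervention, so exits before the session do not enter it. Even if 3 exits were added to an illustrative 14 schedulers, 14/45 = 31.1% becomes 14/48 = 29.2%, against an exact 95% interval for 14/45 of 18.2% to 46.6%.

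**The case for a change.** The strongest reply is that a feasibility pilot should state its retention denominator because retention is a main result. The voluntary and study-decided exits stand in adjacent sentences, and only the first has a data rule, so a reader cannot tell whether the omission was meant. The plan also does not say whether someone lost to follow-up counts as withdrawn and is replaced. One added sentence would cost nothing.

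Part of this stands. The data rule is literally limited to people who choose to leave, and all enrolled is never written down. The timing of the Section 11 exclusion is also unclear. Section 17 says suicidal risk is assessed at screening, yet Section 9 lets the PHQ-9 fall to baseline, after enrolment. Sections 9, 11 and 17 must be reconciled on that by those responsible for the clinical procedures; I take no view on what the rule should be.

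The rest is weaker. Section 11 uses the language of screening and exclusion, and Section 6 has a related exclusion criterion for imminent danger. For danger identified at any time, Section 17 describes support and referral, with no exclusion or replacement. An exclusion after enrolment is therefore an inference. The alcohol-first scenario also relies on the order shown in Section 9, which refers to a list absent from the text supplied. Loss to follow-up affects how many are enrolled in total, but not who belongs in an all-enrolled denominator.

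**Conclusion.** No change to the analysis plan is needed. An analyst following it as written would count replacements as additional to 45, take eligibility from the screening decision, compute completion over all enrolled, and treat data from removed subjects like data from those who withdrew. That gives a sound completion percentage. The higher figure of 100% arises only if exits are reclassed or dropped, which no section directs.

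The size is small under the assumed exits: 6.2 percentage points of completion with 3, and 2.2 points (100 − 97.8) with 1. It would be larger if exits were frequent, but the ordinary reading is the same at any rate. The plan sets no completion threshold for going on to a randomized trial, so no stated decision turns on the difference. No bias in the scheduling proportion is shown.

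This conclusion rests on reading Section 18's subjects as everyone enrolled and on nothing in the unseen consent form directing that removed subjects' data be discarded. The uncertain timing of the Section 11 exclusion is procedural and changes no figure in the plan.
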